6 STUDY REGIMEN PRODUCTS

6.1 Product Ingredients

SkinMedica® Facial Cleanser Ingredients:

Water/Aqua/Eau, Disodium Laureth Sulfosuccinate, Cocamidopropyl, Hydroxysultaine, Sodium Lauryl Sulfoacetate, Camellia Oleifera Leaf Extract, Glycerin, Panthenol, Butylene Glycol, Ethylhexylglycerin, PEG-150 Pentaerythrityl Tetraostearate, PEG-6 Caprylic/Capric Glycerides, Disodium EDTA, Phenoxyethanol, Parfum/Fragrance, Blue 1 (CI 42090), Yellow 10 (CI 47005)

SkinMedica® Retinol Complex 0.5 (Test product)

Water/Aqua/Eau, Cetyl Ethylhexanoate, Glycine Soja Oil, Caprylic/Capric Triglyceride, Niacinamide, Polyacrylate-13, Squalane, Retinol, Palmitoyl Tripeptide-8, Dunaliella Salina Extract, Magnolia Grandiflora Bark Extract, Tocopherol, Tocotrienols, Ceramide 3, Bisabolol, Phytosterols, Squalene, Tocopheryl Acetate, Oryza Sativa Bran Cera, Glycerin, Polysorbate 20, Butylene Glycol, Cetyl Palmitate, Laureth-23, Trideceth-6 Phosphate, Sodium Hydroxide,

Dicaprylyl Ether, Lauryl Alcohol, Polyisobutene, Dextran, Potassium Sorbate, Disodium EDTA, Phenoxyethanol, Ethylhexylglycerin

Cetaphil Moisturizing Lotion

Water, glycerin, hydrogenated polyisobutene, cetearyl alcohol, ceteareth-20, Macadamia integrifolia seed oil (macadamia nut oil), dimethicone, tocopheryl acetate, stearoxytrimethylsilane, stearyl alcohol, panthenol, farnesol, benzyl alcohol, phenoxyethanol, acrylates/C10-30 alkyl acrylate crosspolymer, sodium hydroxide, citric acid

Essential Defense Mineral Shield Sunscreen SPF35

Active Ingredients: Titanium dioxide 5.0%, Zinc oxide 6.0%

Inactive Ingredients: Water, Cyclopentasiloxane, Dimethicone, Polyglyceryl-3 Polydimethylsiloxylethyl Dimethicone, Butylene Glycol, Aluminum Hydroxide, Dimethicone/PEG-10/15 Crosspolymer, PEG-9 Polydimethylsiloxylethyl Dimethicone, Sodium Chloride, Caffeine, Camellia oleifera Leaf Extract, Tocopheryl Acetate, Sodium Citrate, Dimethicone/Vinyl Dimethicone Crosspolymer, Triethoxysilylethyl Polydimethylsiloxylethyl Hexyl Dimethicone, PEG/PPG-18/18 Dimethicone, Triethoxycaprylylsilane, Stearic Acid, Ethylhexylglycerin, Phenoxyethanol, Iron Oxides (CI 77491, CI 77492, CI 77499)

6.2 Warnings, Precautions and Contraindications

These study products are for topical use only. Care should be taken to avoid contact with eyes and all mucous membranes. If contact with eyes occurs, rinse thoroughly with water.

Mild redness, peeling and irritation are expected when using this product. Use of a sunscreen and limiting sun exposure is required while using the test product and for a week following discontinuation.

Subjects with a known allergy to any of the ingredients in the study products should not participate in this study.

There are no adequate and well-controlled studies of the Study Product ingredients in pregnant women. Also, it is not known whether the ingredients are excreted in human milk following use of topical products containing these ingredients. Women who are pregnant or lactating will be excluded from this study. Women of childbearing potential must not be pregnant or planning a pregnancy during the study period.

In case of accidental ingestion, subjects should contact the study staff immediately.

6.3 Storage, Handling and Dispensing the Study Medication

All study products should be stored at controlled room temperature

6.4 Subject Regimen and Dosing Instructions

Wash-out period (2 weeks prior to Baseline)

- Every morning (AM):

1. Subjects will gently wash their facial skin with Facial Cleanser.
2. Apply approximately a nickel-sized amount of Cetaphil Moisturizing Lotion to their facial skin.

- 3. Apply Essential Defense Mineral Shield Sunscreen SPF 35 to their face and re-apply as needed throughout the day.
- Every evening (PM):
 1. Subjects will gently wash their facial skin with Facial Cleanser.
 2. Apply approximately a nickel-sized amount of Cetaphil Moisturizing Lotion to their facial skin.
- Subjects may apply cosmetic make-up if applicable.

The Test Product will be packaged in 1 oz. bottles with a pump. Subjects will apply the Test Product onto their facial skin once a day in the evening as per the below instructions:

- Every morning (AM):
 1. Subjects will gently wash their facial skin with Facial Cleanser.
 2. Apply approximately a nickel-sized amount of Cetaphil Moisturizing Lotion to their facial skin.
 3. Apply Essential Defense Mineral Shield Sunscreen SPF 35 to their face and re-apply as needed throughout the day.
- Every evening (PM):
 1. Subjects will gently wash their facial skin with Facial Cleanser.
 2. Immediately after cleansing, subjects will apply a nickel-sized amount of the Test Product onto their entire face avoiding the eye area. Product should not be applied on the eyelid. Care should be taken to prevent product from getting into the eyes. Allow product to absorb (30 seconds to 1 minute).
 3. Apply approximately a nickel-sized amount of Cetaphil Moisturizing Lotion to their facial skin.
- Subjects may apply cosmetic make-up if applicable.

Subjects will use the Test Product starting on the evening of the baseline visit.

Subjects will use the SkinMedica Facial Cleanser starting at the screening visit to remove makeup and cleanse the face.

6.5 Dose Modifications

Modifications of the Test Product dosing are allowed at the discretion of the investigator. If irritation develops, subjects will be instructed to contact the study staff.

7 RANDOMIZATION ASSIGNMENT

N/A

8 PRIOR AND CONCOMITANT THERAPIES

8.1 Prohibited Medications or Therapies

Medications or treatments that are prohibited during the duration of the study are as follows:

Prior to entry, into the study, subjects must not have:

- Used systemic retinoids at least 12 months prior to study entry.
- Used topical retinoids and/or all other topical medication (topical steroids, products containing benzoyl peroxide, alpha- or beta-hydroxy acids, hydroquinone, and/or any other OTC skin treatments to the facial area at least 14 days prior to study entry.
- Received a laser treatment of the face within 6 months prior to study entry.
- Received microdermabrasion or a chemical peel within 30 days of study entry.

- Been treated with another investigational device or drug within 30 days prior to study entry.

During the study, other chronic medications being used at the time of Screening Visit, with the exception of those specified in Section 5.1.2. can be continued at the discretion of the investigator.

[figure not shown]
Subjects may not use any other topical products other than those provided for the study. The reason for any changes in concomitant therapies should be reported as, or in conjunction with, an adverse event.

8.2 Allowed Medications or Treatments

No additional medications, including over-the-counter preparations, should be used without the knowledge and, if possible, permission of the investigator. Vitamins and mineral supplements are permitted at dosages considered by the investigator as reasonable for maintaining good health. The addition, discontinuation, or dose change of any concomitant medications will be documented in the source documents.

Medications will be permitted, at the discretion of the investigator, to treat local skin reactions, if applicable.

Cosmetic make-up can be used during the study as long as they meet exclusion criteria #8, and if the subjects has regularly used (defined as products used for a minimum of 2 weeks prior to enrollment) the make-up without any incidence of irritation.

10 CLINICAL EVALUATIONS

The following clinical evaluations will be performed according to the schedule indicated during the study. The same grader should conduct the efficacy assessments for a subject at all visits, to prevent variations in grading.

10.1 Clinical Assessments

10.1.1 Investigator Assessments

Clinical efficacy assessments of the face will be performed as follows at all visits, unless otherwise specified. Whole numbers are allowed only (i.e. no half-points, or plus or minus designations).

Overall Photodamage (0-9 scale)

- None (0) = Facial skin is smooth to the touch, without significant fine/coarse lines or skin tone unevenness in any areas (periocular area, cheeks, forehead, and perioral area)
- Mild (1- 3) = Facial skin shows 1 area (periocular area, cheeks, forehead, and perioral area) of significant roughness, or skin tone unevenness (red/brown), or fine/coarse lines
- Moderate (4- 6) = Facial skin shows 2 areas (periocular area, cheeks, forehead, and perioral area) of significant roughness, skin tone unevenness (red/brown), or fine/coarse line
- Severe (7- 9) = Facial skin shows 3 or more areas (periocular area, cheeks, forehead, and perioral area) of significant roughness, skin tone unevenness (red/brown), or fine/coarse lines

Skin Roughness (0-4 scale)- Allergan Skin Roughness Visual Scale (Refer to Appendix I)

- None (0) = Smooth visual skin texture
- Minimal (1) = Slightly coarse and uneven visual skin texture
- Moderate (2) = Moderately coarse and uneven visual skin texture; may have early elastosis
- Severe (3) = Severely coarse visual skin texture, crosshatched fine lines; may have some elastosis
- Extreme (4) = Extremely coarse visual skin texture, crosshatched deep creases; extreme elastosis

Tactile Roughness (0-9 scale entire face)

- None (0) = No roughness of the treatment area; skin is completely smooth and pliable

- Mild (1-3) = Some areas of slightly irregular roughness in the treatment area
- Moderate (4-6) = Several areas of definite roughness of the treatment area
- Severe (7-9) = Marked roughness of the treatment area associated with stiff feeling

Fine Lines (0-4 scale) - Allergan Fine Lines Visual Scale (Appendix II)

- None (0) = No fine lines
- Minimal (1) = 1-2 superficial lines
- Moderate (2) = 3-5 superficial lines
- Severe (3) = Greater than 5 superficial lines; no crosshatching
- Diffuse (4) = Diffuse superficial lines; crosshatching

Fine Lines/Wrinkles - Forehead, Periocular, Cheeks, Perioral areas individually assessed (0-9 scale) (Refer to Appendix III)

- None (0) = No fine lines/wrinkles present; skin looks completely smooth and wrinkle-free
- Mild (1-3) = Rare, presence of fine lines and wrinkles, widely spaced apart in the treatment area
- Moderate (4-6) = Moderate number of fine lines/wrinkles in close proximity to each other in the treatment area
- Severe (7-9) = Many fine lines/wrinkles densely packed together in the treatment area

Coarse Lines/Wrinkles - Forehead, Periocular, Cheeks, Perioral areas individually assessed (0-9 scale) (Refer to Appendix III)

- None (0) = No coarse lines/wrinkles present; skin looks completely smooth and wrinkle-free
- Mild (1-3) = Rare, presence of coarse lines and wrinkles, widely spaced apart in the treatment area
- Moderate (4-6) = Moderate number of coarse lines/wrinkles in close proximity to each other in the treatment area
- Severe (7-9) = Many coarse lines/wrinkles densely packed together in the treatment area

Global Improvement in Photodamage (0-4 scale; at follow-up visits only)

- None (0) = No change or worsening
- Mild (1) = A noticeable improvement of the condition with a distinctive amount of signs/symptoms remaining (approximately 25% overall improvement)
- Moderate (2) = A very noticeable improvement of the condition with a fair amount of signs/symptoms remaining (approximately 50% overall improvement)
- Marked (3) = A distinctive improvement of the condition with some signs/symptoms remaining (approximately 75% overall improvement)
- Complete (4) = Almost complete improvement of the condition with a trace of signs/symptoms remaining (approximately 95% or better overall improvement)

Global Improvement in Fine Lines/Wrinkles – Forehead, Periocular, Cheeks, Perioral areas individually assessed (0-4 scale; at follow-up visits only)

[figure not shown]
- None (0) = No change or worsening
- Mild (1) = Mild improvement in the appearance of fine lines/wrinkles (approximately 25% overall improvement)
- Moderate (2) = Moderate improvement in the appearance of fine lines/wrinkles (approximately 50% overall improvement)
- Marked (3) = Marked improvement in the appearance of fine lines/wrinkles (approximately 75% overall improvement)
- Complete (4) = Complete clearing in the appearance of fine lines/wrinkles (approximately 95% or better overall improvement)

Global Improvement in Coarse Lines/Wrinkles – Forehead, Periocular, Cheeks, Perioral areas individually assessed (0-4 scale; at follow-up visits only)

- None (0) = No change or worsening
- Mild (1) = Mild improvement in the appearance of coarse lines/wrinkles (approximately 25% overall improvement)
- Moderate (2) = Moderate improvement in the appearance of coarse lines/wrinkles (approximately 50% overall improvement)
- Marked (3) = Marked improvement in the appearance of coarse lines/wrinkles (approximately 75% overall improvement)
- Complete (4) = Complete clearing in the appearance of coarse lines/wrinkles (approximately 95% or better overall improvement)

Global Improvement in Tactile Roughness (0-4 scale; at follow-up visits only)

- None (0) = No change or worsening
- Mild (1) = Mild improvement in the appearance of tactile roughness (approximately 25% overall improvement)
- Moderate (2) = Moderate improvement in the appearance of tactile roughness (approximately 50% overall improvement)
- Marked (3) = Marked improvement in the appearance of tactile roughness (approximately 75% overall improvement)
- Complete (4) = Complete clearing in the appearance of tactile roughness (approximately 95% or better overall improvement)

10.1.3 Instrumentation

Standardized digital photography will be taken of the subject's left, right and frontal facial views with the [REDACTED]

Triplicate 3D images of a designated area on the face will be taken with the [REDACTED] at baseline and all follow-up visits.

Non-invasive *in vivo* skin imaging will be conducted with the [REDACTED] and [REDACTED] on a designated target area on the face at baseline and all follow-up visits.

Triplicate measurements of the facial skin at a target location will be taken using a [REDACTED] at baseline and all follow-up visits.

10.2 Adverse Events

Adverse events (AEs) will be recorded in the AE section of the source documents. The start of adverse event collection will take place immediately after the subject completes their Screening visit (Day 0). Definitions and reporting requirements for serious AEs are depicted in Section 13.0.

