Study Regimen	
Subjects will be instructed to remove all makeup from the face and cleanse the face at least 15 minutes prior to investigator assessments and use of skin instrumentation.
 
 For standardization, this procedure will be performed with SkinMedica Facial Cleanser (to remove makeup and cleanse the face) for all the subjects. 
Take home regimen during 2 week wash out period:
 
 1. SkinMedica Facial Cleanser (AM and PM) 2. Cetaphil Fragrance Free Moisturizing Lotion (AM and PM) 3. SkinMedica Essential Defense Mineral Shield Broad Spectrum SPF 35 Sunscreen (AM and as needed) 
Take home regimen (Baseline – Week 12):
 
 1. SkinMedica Facial Cleanser (AM and PM) 2. SkinMedica Retinol Complex 0.5 (PM) 3. Cetaphil Fragrance Free Moisturizing Lotion (AM and PM) 4. SkinMedica Essential Defense Mineral Shield Broad Spectrum SPF 35 Sunscreen (AM and as needed)
Study Design	[REDACTED]

	
	
Subjects will complete multiple questionnaires including a self-assessment questionnaire on the test product, and questionnaires regarding their aging appearance, lines, satisfaction with their skin, social confidence, and psychological well-being.
 
Any subject compensation will be provided to the subject at this visit.

Treatment Groups	After enrollment into the study and completion of the wash-out regimen, all subjects will receive the Test Product.

Duration of Study	Study Start Date: August 2017 Study End Date: August 2018
Study Population	Male or female subjects with Fitzpatrick skin types I-IV, ages 40-70 years old with moderate to severe facial photodamage.
Total Number of Subjects	Up to 50 subjects will be enrolled into the study.
Number of Sites	One site

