3 OBJECTIVES

To assess the cosmetic changes of a cosmetic topical retinoid product in subjects with moderate to severe photodamage utilizing skin imaging instrumentation.

Safety will be evaluated by adverse events reported during the study.

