13 ADVERSE EVENT REPORTING

13.1 Adverse Events

Any clinical findings determined by the Investigator to be important and/or unusual will be referred to as an adverse event (AE). Subjects are asked to contact the clinic staff immediately if they experience a reaction at any time during the study. The subject may be examined by the clinic's staff or by the study physician. The start of adverse event collection for this study will be immediately after the subject completes their Screening visit.

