14.2 Study Basic Skincare Products

- SkinMedica Facial Cleanser [SkinMedica, Inc., an Allergan Company]
- Cetaphil Moisturizing Lotion [Galderma Laboratories, L.P.]
- SkinMedica Essential Defense Mineral Shield Broad Spectrum SPF 35 [SkinMedica, Inc., an Allergan Company]

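### Adverse event collection opens only after the Screening visit ends, so a reaction to the supplied cleanser that begins during that visit need not be recorded

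*Combined protocol and SAP*

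**What the plan says.** The start of collection is set in two places. Section 10.2: "The start of adverse event collection will take place immediately after the subject completes their Screening visit (Day 0". Section 13.1: "The start of adverse event collection for this study will be immediately after the subject completes their Screening visit".

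First use of a supplied product is set in section 6.4: "Subjects will use the SkinMedica Facial Cleanser starting at the screening visit to remove makeup and cleanse the face". The Study Regimen row of the synopsis asks subjects to remove makeup and "cleanse the face at least 15 minutes prior to investigator assessments and use of skin instrumentation", and adds that "this procedure will be performed with SkinMedica Facial Cleanser (to remove makeup and cleanse the face) for all the subjects". Section 14.2 lists the cleanser among the study's basic skincare products.

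The Test Product comes later: "Subjects will use the Test Product starting on the evening of the baseline visit" (section 6.4), after a 2-week wash-out on cleanser, moisturizer and sunscreen.

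On safety, section 3 says: "Safety will be evaluated by adverse events reported during the study". Section 16.3 analyses adverse events by incidence and severity.

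**The concern.** The plan exposes every subject to a supplied product before it opens the adverse event record. The protocol treats the cleanser as a study product: section 6.1 gives its ingredients, known sensitivity to the ingredients of study products is an exclusion (section 5.1.2), and the eye-contact precaution in section 6.2 covers all study products. Stinging or eye irritation at the first wash is thus an event the plan foresees, but the rule does not require it to be captured. At stake is whether the adverse event record for the basic regimen is complete from first exposure. Efficacy is not involved.

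**Working it through.** The protocol states no figure that bears on this point, so there is nothing to recalculate. The check is to put the stated times in order.

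1. **Consent.** Sections 17.1 and 17.2 require it before any study procedure, so it precedes the first study wash.
2. **First use of the cleanser.** Section 6.4 places it at the Screening visit. The synopsis applies the pre-assessment wash to all subjects.
3. **Assessments at Screening.** The synopsis and section 10.1.1 schedule investigator assessments at all visits, with exceptions marked. The synopsis puts cleansing at least 15 minutes before them. If that holds at Screening, at least 15 minutes pass between first use and the end of the visit.
4. **End of the Screening visit.** Adverse event collection opens (sections 10.2 and 13.1).
5. **Wash-out, 2 weeks.** Cleanser, moisturizer and sunscreen at home; collection is open.
6. **Baseline visit.** First Test Product application that evening; collection has been open for about 2 weeks.

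The uncovered interval runs from step 2 to step 4. It contains exposure to the cleanser and none to the Test Product.

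**Is Screening part of the study?** Section 12.1 defines completion as 5 visits. Section 15 names four: Baseline, Week 4, Week 8 and Week 12. The remainder is 5 − 4 = 1, which fits Screening. The visit schedule is not in the public text, so this is an inference. If it is right, the start rule omits part of the study over which section 3 evaluates safety.

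**Does other text close the gap?** Section 13.1 asks subjects to report reactions whenever they occur, but the same section fixes the later start. Section 13.3 requires all adverse events to be recorded, but does not say that this reaches back before collection opens. Section 13.2 counts a condition that worsens during the study, which helps only if the reaction gets worse. None of these overrides the start rule.

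**The case against.** The strongest reply is that the gap is too small to matter. It concerns one wash with a commercially available cleanser, used to standardize the assessments. The Test Product, which is what the study evaluates, is first applied well inside the collection period. The analysis population in section 16.2 requires use of the Test Product, so screening failures would not enter it. Sections 10.2 and 13.1 agree with each other, so this is a stated choice and not a contradiction between them. All of this stands, and it limits the point to a minor one.

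A second reply is that the place of the first wash is not settled. Inclusion criterion 5 speaks of cleansing before each visit, and the visit schedule is not shown. This stands in part, and makes the length of the interval uncertain. But section 6.4 ties first use of the supplied cleanser to the Screening visit, and a wash before arrival with that product would fall outside collection too.

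A third reply is that a notable reaction would probably be noticed and noted, through the reporting duty or the eligibility examination. That is plausible. It means only that such a reaction may be written down somewhere, not that it must be entered as an adverse event.

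**Conclusion.** The point holds in a narrow form. Under sections 10.2 and 13.1, a reaction with onset between first use of the supplied cleanser and the end of the Screening visit is not required to be recorded as an adverse event. This applies by design to every subject. It rests on reading section 6.4 and the synopsis as placing the first wash within that visit, which is their most natural meaning.

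The likely effect on conclusions about Test Product safety is negligible. Four stronger readings might be inferred, and the documents do not support them:

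- **That first-exposure reactions in general are lost.** Reactions to the first wash that begin after the visit are collected, as are those during wash-out and on the Test Product.
- **That the missed events can be counted.** An assumed immediate-reaction rate of 0 to 4% among the maximum of 50 enrolled subjects gives 50 × 0 = 0 to 50 × 0.04 = 2. No document supports that rate, the range includes zero, and screening failures would come on top of the 50.
- **That such events are never recorded.** The rule does not require an adverse event entry; it does not forbid a note elsewhere.
- **That a persisting reaction would be dismissed as pre-existing under section 13.2.** That section does not define the pre-study period, and a reaction at a study visit after consent need not be read that way.

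**What to change.** In sections 10.2 and 13.1, replace the start rule with one sentence, for example: *Adverse event collection begins no later than the first use of any study-supplied product.* Signing of informed consent is a convenient anchor, since sections 17.1 and 17.2 already place it before any procedure; it is somewhat broader than the gap strictly needs. In section 16.3, add that events with onset before the first Test Product application are listed separately, so that events on the basic regimen do not add to the Test Product's incidence.

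The cost is a small amount of extra recording, including for subjects who fail screening, and one extra listing. No visit or assessment is added. As an amendment it needs ethics approval under section 17.4, so it is sensibly bundled with other changes.
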